6.5.5.2 Follow up for sabatolimab & NIS793

The emergence of Immune-Related AE (irAE) may be anticipated based on general experience in clinical studies with similar class of compounds that block the negative immune regulators.

An irAE is a clinically significant AE affecting any organ that is associated with study drug exposure, is consistent with an immune-mediated mechanism, and where alternative explanations have been investigated and ruled out or are considered unlikely.

Subjects should be monitored carefully for any skin toxicity or mucositis and study treatment should be discontinued for any suspected case of SJS/TEN.

Serologic, histologic and immunological assessments should be performed as deemed appropriate by the Investigator, to verify the immune-related nature of the AE.

All subjects with signs or symptoms of irAEs should be monitored and managed following the consensus guidelines from NCCN, ASCO or ESMO for the management of immune-related adverse events as outlined in Section 6.5.4

Patients whose treatment is interrupted or permanently discontinued due to an irAE, AE or clinically significant laboratory value, must be followed-up at least once a week (or more frequently if required by institutional practices, or if clinically indicated) for 4 weeks, and subsequently at approximately 4-week intervals, until resolution or stabilization of the event, whichever comes first. Appropriate clinical experts should be consulted as deemed necessary.

In case of a suspected irAE, the relevant immunological assessments (e.g. rheumatoid factor, anti-DNA Ab, etc.) should be performed. In case of a toxicity suspected to be a cytokine release syndrome, the assessments outlined in Section 8 (Table 8-2, Table 8-3, Table 8-4 & Table 8-5) must be performed. All patients must be followed up for irAEs, AEs and SAEs for 90 days following the last dose of NIS793 in combination with ruxolitinib, and for 105 days following the last dose of sabatolimab in combination with ruxolitinib.

For any AE/AEs Grade 1 and/or Grade 2, treatment with sabatolimab should be maintained at the determined dose and schedule, unless otherwise specified in Table 6-7. Similarly,

For any AE/AEs Grade 1 and/or Grade 2, treatment with NIS793 should be maintained at the determined dose and schedule, unless otherwise specified in

Follow up on potential drug-induced liver injury (DILI) cases

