9.2 Study completion

All subjects receiving combination treatment must have a Safety Follow-up visit at least 30 days (+7 days) after the last dose of study treatment (all investigational drugs) to have hematology, chemistry, vital signs and serum pregnancy assessments and to collect information on any AEs, concomitant medications, transfusions, non-drug therapies and procedures, and anti-neoplastic therapies. Additional Safety Follow-up visits should also occur, as follows:

- 105 days (+7 days) after the last dose of crizanlizumab for subjects on ruxolitinib + crizanlizumab (or crizanlizumab monotherapy in Part 3)
- 90 days (+7 days), and 150 days (+14 days) after the last dose of sabatolimab for subjects on ruxolitinib + sabatolimab (or sabatolimab monotherapy in Part 3).
- 90 days (+7 days) after the last dose of NIS793 for subjects on ruxolitinib + NIS793 (or NIS793 monotherapy in Part 3).

The timing of the final Safety Follow-up visit is based on a period of at least 5 times the halflife of crizanlizumab, sabatolimab, and NIS792 after the last dose when the serum level of crizanlizumab, sabatolimab, and NIS793 in all subjects should be negligible or below the LLOO.

At the 90-, 105-, and 150-day Safety Follow-up visits, the same assessments will be performed as per the 30-day Safety Follow-up visit. The planned PK sample and IG sample will not be collected at the 90-day Safety Follow-up visit for sabatolimab, and at the 105-day Safety Follow-up visit for crizanlizumab, due to enrollment halt. For NIS793, the planned PK, PD and IG samples will not be collected at the 30-day and 90-day Safety Follow-up visits, due to enrollment halt. However, if the subject begins new antineoplastic medication (other than study treatment) before the end of the safety follow-up period, the collection of new SAEs and AEs unrelated to study medication will stop and thereafter only suspected AEs and suspected SAEs will continue to be collected up to the end of the safety follow-up period.

Refer to Table 8-2, Table 8-3, Table 8-4 and Table 8-5 for a complete list of the assessments to be completed at the Safety Follow-up visits. The information collected is kept as source documentation. All SAEs reported during this time period must be reported as described in Section 10.1.3. Documentation of attempts to contact the subject should be recorded in the source documentation.

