If the event worsens the event should be reported a second time in the CRF noting the start date when the event worsens in toxicity. For grade 3 and 4 adverse events only, if improvement to a lower grade is determined a new entry for this event should be reported in the CRF noting the start date when the event improved from having been Grade 3 or Grade 4.

Conditions that were already present at the time of informed consent should be recorded in medical history of the subject.

Adverse events (including lab abnormalities that constitute AEs) should be described using a diagnosis whenever possible, rather than individual underlying signs and symptoms.

Adverse event monitoring should be continued for at least:

- 30 days after the last dose of single-agent ruxolitinib (control/monotherapy)
- 30 days after the last dose of ruxolitinib or siremadlin for subjects on ruxolitinib + siremadlin (or siremadlin monotherapy in Part 3)
- 30 days after the last dose of ruxolitinib or rineterkib for subjects on ruxolitinib + rineterkib (or rineterkib monotherapy in Part 3)
- 90 days after the last dose of NIS793 for subjects on ruxolitinib + NIS793 (or NIS793 monotherapy in Part 3)
- 105 days after the last dose of crizanlizumab for subjects on ruxolitinib + crizanlizumab (or crizanlizumab monotherapy in Part 3)
- 150 days after the last dose of sabatolimab for subjects on ruxolitinib + sabatolimab (or sabatolimab monotherapy in Part 3).

OR

until the start of a new post treatment anti-neoplastic medication if sooner than the end of the safety follow-up period mentioned above, depending on the study treatment. If a subject starts post treatment antineoplastic medication, then only adverse events suspected to be related to study treatment should be collected, up to the end of the safety follow-up period noted above.

Progression of the underlying disease (myelofibrosis) (including fatal outcomes) based on the criteria described in Section 8.3.2.3 (ie. progressive splenomegaly, increase in peripheral blood blast content of > 10% (accelerated phase), deteriorating cytopenia, leukemic transformation) should not be reported as a serious adverse event. These disease progression events will be reported on specific CRF pages other than the AE CRF.

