The study day will be displayed in the data listings. If an event starts before the reference start date, the study day displayed on the listing will be negative.

Time unit

A year length is defined as 365.25 days. A month length is 30.4375 days (365.25/12). If duration is reported in months, duration in days will be divided by 30.4375. If duration is reported in years, duration in days will be divided by 365.25.

Baseline

For safety and efficacy evaluations, the last available assessment on or before the date of start of study treatment is defined as “baseline” assessment.

In case time of assessment and time of treatment start is captured (e.g. pre-dose ECG), the last available assessment before the treatment start date/time is used for baseline.

For safety parameters (e.g ECGs or vital signs), where study requires multiple replicates per time point, the average of these measurements would be calculated for baseline (if not already available in the database).

If patients have no value as defined above, the baseline result will be missing.

On-treatment assessment/event and observation periods

The overall observation period will be divided into three mutually exclusive segments:

1. ***pre-treatment period***: from day of subject's informed consent to the day before first administration of study treatment
2. ***on-treatment period***: from date of first administration of study treatment to 30 days after date of last actual administration of any study treatment (including start and stop date)
3. ***post-treatment period***: starting at day 31 after last administration of study treatment.

Moreover, ***on-extension treatment period*** is defined from day of first administration of extension phase study treatment to 30 days after the date of the last administration of study treatment.

In addition, the ***overall safety period*** is defined for this study as following:

Overall safety period: from date of first administration of study treatment to 30 days after the date of the last administration of ruxolitinib, siremadlin or rineterkib, 90 days after the date of the last administration of NIS793, or 105 days after the date of the last administration of crizanlizumab, or 150 days after the date of the last administration of sabatolimab, whichever is later.

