2.8.1.1 Adverse events of special interest / grouping of AEs

Adverse events of special interest (AESI) during the on-treatment period will be tabulated. The list of AESI will also include relevant events for ruxolitinib, and the novel agents including but not limited to sitemartin, crizanlizumab, sabatolimab and NIS793, if deemed appropriate.

Data analysis of AESIs

An adverse event of special interest is a grouping of adverse events that are of scientific and medical concern specific to compound ruxolitinib and the individual novel agents, if deemed appropriate. These groupings are defined using MedDRA terms, SMQs (standardized MedDRA queries), HGLTs (high level group terms), HLT (high level terms) and PTs (preferred terms). Customized SMQs (Novartis MedDRA queries, NMQ) may also be used. A NMQ is a customized group of search terms which defines a medical concept for which there is no official SMQ available or the available SMQ does not completely fit the need. It may include a combination of single terms and/or an existing SMQ, narrow or broad. All AESI terms for the individual compounds as well as for combination specific AESIs, if deemed appropriate, are captured in the case retrieval strategy/strategies (CRS).

For each specified AESI, number and percentage of patients with at least one event of the AESI occurring during on treatment period will be summarized. Summaries of these AESIs will be provided by treatment arm, (specifying grade, SAE, relationship, action taken, medication or therapy taken, AE outcome). A listing of all grouping levels down to the MedDRA preferred terms used to define each AESI will be generated.

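### AESI tables stop 30 days after the last study dose, so late events in the antibody arms, though still reported elsewhere, are left out of the AESI groupings (minor)

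*SAP*

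**What the plan says.** SAP 2.8.1.1 restricts AESIs to one window and says so twice: "Adverse events of special interest (AESI) during the on-treatment period will be tabulated", and "number and percentage of patients with at least one event of the AESI occurring during on treatment period will be summarized". These summaries are broken down by grade, seriousness, relationship, action taken, therapy given and outcome. The groupings are built from MedDRA queries and term levels, held in a separate case retrieval strategy.

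SAP 2.1.1 defines the on-treatment period as running "from date of first administration of study treatment to 30 days after date of last actual administration of any study treatment". It also defines a longer overall safety period. For two of the antibodies this ends "90 days after the date of the last administration of NIS793, or 105 days after the date of the last administration of crizanlizumab"; for sabatolimab the limit is 150 days from its final dose, and the latest applicable date governs.

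Protocol 10.1.1 collects AEs on matching windows, for example "90 days after the last dose of NIS793 for subjects on ruxolitinib + NIS793". Protocol 9.2 ties these windows to the half-lives of the antibodies: "The timing of the final Safety Follow-up visit is based on a period of at least 5 times the". By five half-lives, serum drug is expected to be negligible or under the quantification limit.

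SAP 2.1.1 and 2.8.1 summarise all AEs and SAEs over the overall safety period. They also list every AE, with those starting after the on-treatment period flagged. No AESI summary over that period is planned. The SAP change history (entry of 30-Nov-2022) records that such summaries were removed, without giving a reason.

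**The concern.** An AESI grouping brings related preferred terms together so that a known drug risk can be counted per patient. In the antibody arms the plan treats patients as still exposed well beyond day 30 and follows them accordingly, yet this drug-specific table stops at day 30. Two patients with related late events coded to different terms would appear as two single-patient rows in the general AE table. They would not appear as two patients with that AESI.

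The siremadlin and rineterkib arms have no such gap, because their AE follow-up is itself 30 days. For sabatolimab and NIS793, Protocol 6.5.5.2 states: "The emergence of Immune-Related AE (irAE) may be anticipated based on general experience in clinical studies with similar class of compounds". Protocol 4.5 also calls immune-related events an anticipated risk for these two agents. What is at stake is how complete the AESI count is in those arms. DLT assessment and dose selection are not affected.

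**Working it through.** The documents state no figure for the gap, so it is derived from the windows.

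**Inputs**
- Antibody safety window W, in days after the last antibody dose: NIS793 90, crizanlizumab 105, sabatolimab 150 (SAP 2.1.1; Protocol 10.1.1).
- The on-treatment period ends 30 days after the last dose of any study treatment, ruxolitinib included (SAP 2.1.1).
- k = days that ruxolitinib continues after the last antibody dose. The documents do not give k, so a range is shown.

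**Formula.** Counted from the last antibody dose, the AESI window closes at day 30 + k. Untabulated days = W − (30 + k), with a floor of zero.

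**Case 1: all drugs stop on the same day (k = 0), the maximum**
- NIS793: 90 − 30 = 60 of 90 days (67%)
- Crizanlizumab: 105 − 30 = 75 of 105 days (71%)
- Sabatolimab: 150 − 30 = 120 of 150 days (80%)

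**Case 2: ruxolitinib runs to the end of the last antibody cycle.** This assumes that the last antibody dose was given on Day 1 of that cycle. Then k = 20 for the 21-day NIS793 cycle and k = 27 for the 28-day cycles, the same cycle-end offsets that SAP Table 2-5 uses for exposure.
- NIS793: 90 − 50 = 40 days
- Crizanlizumab: 105 − 57 = 48 days
- Sabatolimab: 150 − 57 = 93 days

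**Case 3: no gap.** Untabulated days reach zero when k ≥ W − 30, that is 60, 75 and 120 days respectively.

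**Where an event in the gap is still reported**
- Overall-safety-period AE and SAE tables: yes, by system organ class and preferred term.
- AE listing: yes, flagged, with relationship and outcome.
- AESI grouping and its breakdown: no.

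**Scale.** Protocol section 3 plans about 6 subjects in each antibody arm, so one patient is 1/6, about 17 percentage points. This shows only how coarse the percentages are; nothing in the documents indicates that a late AESI occurred.

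**A related inconsistency.** Protocol 6.5.5.2 gives 105 days for immune-related and other AE follow-up after sabatolimab, where Protocol 6.5.5, 10.1.1 and 10.1.3 and SAP 2.1.1 give 150. The figures above use 150. The passages must be reconciled.

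**The case against.** The strongest reply is that leaving this summary out was a decision. The change history shows that the team had the overall-period AESI summary and dropped it after the enrollment halt. The choice also fits the SAP's general rule that safety summaries exclude post-treatment data. That stands: this is not an oversight. But no reason is recorded, and the same SAP makes an exception to that rule for all AEs and SAEs.

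The second reply is that nothing is hidden. Late events are in the overall-period tables and flagged listings, and SAP 2.8.1.1 provides a listing of the terms that define each AESI. In arms of about 6, a reader could regroup them by hand. This also stands, and it is why the point is minor.

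Four stronger readings are tempting, and the documents do not support them.
- A reader might infer that late AESIs drop out of the safety analysis. They drop out of one table.
- A reader might take 67%, 71% and 80% as the share of risk missed. They are shares of calendar days after the last dose, in the maximum case. They leave out the planned 24 weeks of treatment, which the AESI tables cover.
- A reader might extend the immune-related argument to crizanlizumab. Neither immune-related statement names it. The risk that Protocol 4.5 discusses for it is infusion-related reactions, searched for within 24 hours of infusion, which a 30-day window would not miss.
- A reader might infer a distorted comparison between arms. Part 1 plans no between-arm test, and a common 30-day rule has its own logic; the longer view is partly supplied by the overall-period AE and SAE tables.

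**Conclusion.** The point holds as a minor one. The AESI count is incomplete for the follow-up that the plan itself defines in the antibody arms, by up to 60, 75 and 120 days for NIS793, crizanlizumab and sabatolimab. The gap narrows or closes according to how long ruxolitinib continues. What is missing is the grouping and its breakdown, not the events.

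The conclusion rests on two assumptions. The first is that some patients stopped ruxolitinib less than 60, 75 or 120 days after their last antibody dose, which the documents neither state nor exclude. The second is that immune-related events are among the AESI terms for sabatolimab and NIS793. The case retrieval strategy is not in the documents, and SAP 2.8.1.1 includes relevant events only where deemed appropriate, so this is an inference.

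One limit remains whatever table is used: under Protocol 10.1.1, once new antineoplastic therapy starts, only events suspected to be related to study treatment are collected.

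**What to change.** In SAP 2.8.1.1, restore one descriptive AESI summary over the overall safety period, placed beside the on-treatment one, with events that start after the on-treatment period marked. It should cover the antibody arms, and at minimum sabatolimab and NIS793. If a further table is not wanted, the lesser change is to flag AESI terms in the existing listing of post-treatment events. If the summary is to stay out, record the reason for its removal in the SAP.

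The cost is one extra output in arms of about 6 subjects and the reversal of a recorded decision. The data, the window and the AESI groupings are already part of the plan, and no existing analysis changes.

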2.8.1.2 Adverse events of clinical trial safety disclosure

For the legal requirements of ClinicalTrials.gov and EudraCT, two required tables on adverse events which are not serious adverse events with an incidence greater than 5% and on serious adverse events and SAE suspected to be related to study treatment will be provided by system organ class and preferred term on the safety set population.

If for a same patient, several consecutive AEs (irrespective of study treatment causality, seriousness and severity) occurred with the same SOC and PT:

- a single occurrence will be counted if there is ≤ 1 day gap between the end date of the preceding AE and the start date of the consecutive AE
- more than one occurrence will be counted if there is > 1 day gap between the end date of the preceding AE and the start date of the consecutive AE

For occurrence, the presence of at least one SAE / SAE suspected to be related to study treatment / non SAE has to be checked in a block e.g., among AE's in a ≤ 1 day gap block, if at least one SAE is occurring, then one occurrence is calculated for that SAE.

The number of deaths resulting from SAEs suspected to be related to study treatment and SAEs irrespective of study treatment relationship will be provided by SOC and PT.

2.8.1.3 Eye disorders for rineterkib

To assess the eye toxicity of rineterkib, eye disorder AEs (SOC = ‘Eye disorders’) will be summarized by PT and listed for rineterkib combination treatment group.

2.8.2 Deaths

Separate summaries for on-treatment and all deaths (on-treatment and post-treatment) will be produced by treatment arm, primary reason, system organ class and preferred term. All deaths will be listed, post treatment deaths and deaths occurred in the post-treatment overall safety period will be flagged. A separate listing of deaths prior to starting treatment (i.e. during screening period) will be provided for all screened subjects as applicable.

Note: “Study indication” as primary reason of death should be coded using MedDRA terms based on the diagnosis eCRF field at start of study. If not coded accordingly in the database, it still must be included in the summary table. Coded reasons for deaths will then be summarized by category ‘Study indication’ and ‘Other’ (as selected by the investigator).

2.8.3 Laboratory data

Data from all sources (central and local laboratories) will be combined. The summaries will include all laboratory assessments collected no later than 30 days after the last study treatment administration date. Laboratory data will be listed by treatment group, subject, and visit/time and if normal ranges are available abnormalities will be flagged. Summary statistics will be provided by treatment and visit/time. Shift tables using the low/normal/high/ (low and high) classification will be used to compare baseline to the worst on-treatment value.

Grading of laboratory values will be assigned programmatically as per NCI Common Terminology Criteria for Adverse Events (CTCAE) version 5.0. The calculation of CTCAE grades will be based on the observed laboratory values only, clinical assessments will not be taken into account.

CTCAE Grade 0 will be assigned for all non-missing values not graded as 1 or higher. Grade 5 will not be used.

For laboratory tests where grades are not defined by CTCAE v5.0, results will be categorized as low/normal/high based on laboratory normal ranges.

The following summaries will be generated separately for hematology, and biochemistry tests:

- Listing of all laboratory data with values flagged to show the corresponding CTCAE v5.0 grades if applicable and the classifications relative to the laboratory normal ranges. Lab data collected during the post-treatment period will be flagged.
- Listing of all CTCAE grade 3 or 4 laboratory toxicities

For laboratory tests where grades are defined by CTCAE v5.0:

- Worst post-baseline CTCAE grade (regardless of the baseline status). Each subject will be counted only once for the worst grade observed post-baseline.
- Shift tables using CTCAE v5.0 grades to compare baseline to the worst on-treatment value

For laboratory tests where grades are not defined by CTCAE v5.0:

- Shift tables using the low/normal/high/ (low and high) classification to compare baseline to the worst on-treatment value.

Liver function parameters

Liver function parameters of interest are total bilirubin (TBIL), ALT, AST and alkaline phosphatase (ALP). The number (%) of patients with worst post-baseline values as per Novartis Liver Toxicity guidelines will be summarized:

The following summaries will be produced:

- ALT or AST > 3xULN
- ALT or AST > 5xULN
- ALT or AST > 10xULN
- ALT or AST > 20xULN
- ALP > 1.5xULN
- TBL > 2xULN
- ALT or AST > 3xULN & TBL > 2xULN
- ALT or AST > 3xULN & ALP < 2xULN
- ALT or AST > 3xULN & TBL > 2xULN & ALP < 2xULN

